For these first few questions, please think about the person who will come with you to your medical appointment during this study [or who usually comes with you to your medical appointments]. This might be your spouse, your brother/sister, one of your children, or someone else.

- 1. **What is your relationship to this person? You are that person's ____.** **Variable name: relationship**
 - a. Spouse
 - b. Partner
 - c. Mother
 - d. Father
 - e. Brother
 - f. Sister
 - g. Daughter
 - h. Son
 - i. Friend
 - j. Other relationship. Please specify _____

Closeness with Companion

For the next two questions, please continue to think about the person who will come with you to your medical appointment during this study [or who usually comes with you to your medical appointments].

- 1. **Relative to all your other relationships (both same and opposite sex) how would you characterize your relationship with this person?** **Variable name: closeness_1**

Not close at all						Very close
0	1	2	3	4	5	6

2. Relative to what you know about other people's close relationships, how would you characterize your relationship with this person? **Variable name: closeness_2**

Not close at all 0	1	2	3	4	5	Very close 6
-----------------------	---	---	---	---	---	-----------------

Health Literacy

Now I have a couple of questions about how you handle hospital materials and forms.

1. How often do you have someone (like a family member, friend, hospital/clinic worker or caregiver) help you read hospital materials? **Variable name: reading_lit**

None of the time 0	A little of the time 1	Some of the time 2	Most of the time 3	All of the time 4
-----------------------	---------------------------	-----------------------	-----------------------	----------------------

2. How confident are you filling out forms by yourself? **Variable name: fill_forms**

Not at all confident 0	1	2	3	Extremely confident 4
---------------------------	---	---	---	--------------------------

Knowledge of Heart Failure

Next, I would like to find out how much you know about heart failure and its treatment. I'm going to read a question and some possible answers. Tell me which answer you think is correct. If you don't know the answer, you can just say "I don't know."

1. Heart failure means that: **Variable name: meaning**

- a. your heart is beating out of rhythm
- b. your heart might stop beating sometime soon
- c. your heart is not pumping blood as well as it should,
- d. you are having a heart attack
- e. DON'T KNOW

2. Heart failure can cause which of the following problems? **Variable name: signs_sxs**

- a. headache
- b. skin that turns yellow

- c. shortness of breath when you lie down
- d. vomiting blood
- e. DON'T KNOW

3. Which of the following are signs that you are dehydrated (lost too much water)? Variable name: dehydrated

- a. dizziness
- b. shortness of breath
- c. chest pain
- d. peeing a lot
- e. DON'T KNOW

I'm going to read a list of problems, and I want you to tell me whether each one is a sign that heart failure is getting worse. If you don't know the answer, you can just say "I don't know."

4. Is shortness of breath a sign your heart failure is getting worse? Variable name: sob

- a. YES
- b. NO
- c. DON'T KNOW

5. Is swelling of the legs or ankles a sign your heart failure is getting worse? Variable name: swelling

- a. YES
- b. NO
- c. DON'T KNOW

6. What about yellowing of the skin? PROBE: Is yellowing of the skin a sign your heart failure is getting worse? Variable name: yellowskin

- a. YES
- b. NO
- c. DON'T KNOW

Waking up at night short of breath? PROBE: Is waking up at night short of breath a sign your heart failure is getting worse? Variable name: pnd

- a. YES
- b. NO
- c. DON'T KNOW

8. Vomiting blood? PROBE: Is vomiting blood a sign your heart failure is getting worse? Variable name: vomiting

- a. YES
- b. NO
- c. DON'T KNOW

9. Headaches? PROBE: Are headaches a sign your heart failure is getting worse? Variable name: headaches

- a. YES
- b. NO
- c. DON'T KNOW

10. Weight gain? PROBE: Is a gaining weight a sign your heart failure is getting worse? Variable name: wtgain

- a. YES
- b. NO
- c. DON'T KNOW

11. If you eat a lot of salt, it will: Variable name: highsalt

- a. make your heart failure worse
- b. make your heart failure better
- c. have no effect on your heart failure
- d. DON'T KNOW

12. What should you do when you feel more short of breath and your weight has increased by 6 lbs from your good weight? Variable name: knowsxs

- a. stop taking your fluid pill

- b. call your doctor
- c. go on a diet
- d. weigh yourself tomorrow to see if you have gained more
- e. DON'T KNOW

13. What should you do when your legs swell up more than normal? Variable name: legswell

- a. take an extra dose of your fluid pill
- b. walk more
- c. eat more salt
- d. eat more protein
- e. DON'T KNOW

14. Compared to someone without heart failure, a person with heart failure should drink: Variable name: knowdrink

- a. more fluids than usual
- b. about the same amount of fluids
- c. less fluids than usual
- d. DON'T KNOW

15. Someone with heart failure should weigh himself or herself: Variable name: wtfreq

- a. every day
- b. once a week
- c. once a month
- d. only if he or she feels badly
- e. DON'T KNOW

Self-Care Behaviors (Self-Care of Heart Failure Index or SCHFI)

Now, think about how you have been feeling in the **last month** as you respond to these questions.

SECTION A: Listed below are common instructions given to persons with heart failure.

How routinely do you do the following?	Never or rarely	Sometimes	Frequently	Always or daily
1. Weigh yourself? weigh_self	1	2	3	4
2. Check your ankles for swelling? check_ankles	1	2	3	4
3. Try to avoid getting sick (e.g., get a flu shot, avoid ill people)? avoid_sick	1	2	3	4
4. Do some physical activity? phys_activity	1	2	3	4
5. Keep doctor or nurse appointments? keep_appts	1	2	3	4
6. Eat a low salt diet? eat_low_salt	1	2	3	4
7. Exercise for 30 minutes? exercise	1	2	3	4
8. Forget to take one of your medicines? forget_meds	1	2	3	4
9. Ask for low salt items when eating out or visiting others? ask_lowsalt	1	2	3	4
10. Use a system (pill box, reminders) to help you remember your medicines? med_system	1	2	3	4

SECTION B: *sectionb_score*

Many patients have symptoms due to their heart failure. Trouble breathing and ankle swelling are common symptoms of heart failure. *Variable name: schfib_adequate*

In the past month, have you had trouble breathing or ankle swelling? (circle one) *Variable name: trouble*

- 0) No
- 1) Yes

11. If you had trouble breathing or ankle swelling in the past month... (circle one number) *Variable name: freq_trouble*

12.

	Have not had these	I did not recognize it	Not Quickly	Somewhat Quickly	Quickly	Very Quickly
--	--------------------	------------------------	-------------	------------------	---------	--------------

How quickly did you recognize it as a symptom of heart failure? Variable name: quick_recognize	N/A	0	1	2	3	4
--	-----	---	---	---	---	---

Listed below are remedies that people with heart failure use.

If you have trouble breathing or ankle swelling, how likely are you to try one of these remedies? (circle one number for each remedy)	Not Likely	Somewhat Likely	Likely	Very Likely
13. Reduce the salt in your diet reduce_salt	1	2	3	4
14. Reduce your fluid intake reduce_fluid	1	2	3	4
15. Take an extra water pill extra_pill	1	2	3	4
16. Call your doctor or nurse for guidance call_dr	1	2	3	4

17. Think of a remedy you tried the last time you had trouble breathing or ankle swelling

	I did not try anything	Not Sure	Somewhat Sure	Sure	Very Sure
How sure were you that the remedy helped or did not help? sure_remedy	0	1	2	3	4

Self-Efficacy Related to Self-Care

SECTION C:

In general, how confident are you that you can do the following:

	Not Confident	Somewhat Confident	Very Confident	Extremely Confident
18. Keep yourself free of heart failure symptoms? free_sxs	1	2	3	4

19. Follow the treatment advice you have been given? follow_advice	1	2	3	4
20. Evaluate the importance of your symptoms? evaluate_sx	1	2	3	4
21. Recognize changes in your health if they occur? recognize_changes	1	2	3	4
22. Do something that will relieve your symptoms? relieve_sxs	1	2	3	4
23. Evaluate how well a remedy works? evaluate_success	1	2	3	4

Perceived Health Status

1. **How would you rate your overall health? **srh****
 - a. Excellent
 - b. Very good
 - c. Good
 - d. Fair
 - e. Poor

Health Status: Symptom Severity

Which one of the following statements best describes how your heart condition affects you today?
nyha_class

1. Usual physical activity does not cause fatigue, shortness of breath or chest pain. You have no difficulties with usual physical activity
2. Usual physical activity results in fatigue, shortness of breath or chest pain. You have some difficulty with usual physical activity.
3. Less than usual activity causes fatigue, shortness of breath or chest pain. You have great difficulty with usual physical activity.
4. You are unable to do any physical activity without discomfort. Fatigue, shortness of breath or chest pain may be present even at rest.

Communication with Provider

When you visit your doctor, how often do you do the following?

1. Prepare a list of questions for your doctor **make_list**

Never 0	Almost never 1	Sometimes 2	Fairly often 3	Very often 4	Always 5
------------	-------------------	----------------	-------------------	-----------------	-------------

2. Ask questions about your treatment [ask_questions](#)

Never 0	Almost never 1	Sometimes 2	Fairly often 3	Very often 4	Always 5
------------	-------------------	----------------	-------------------	-----------------	-------------

3. Discuss any personal problems that may be related to your illness [discuss_probs](#)

Never 0	Almost never 1	Sometimes 2	Fairly often 3	Very often 4	Always 5
------------	-------------------	----------------	-------------------	-----------------	-------------

Perceived Efficacy in Interacting with Doctor

Next, I'd like to ask you some questions about your interactions with doctors.

1. How confident are you in your ability to know what questions to ask a doctor? [know_to_ask](#)

Not at all confident 0	1	2	3	Very confident 4
------------------------------	---	---	---	---------------------

2. How confident are you in your ability to get a doctor to answer all of your questions?
[get_answers](#)

Not at all confident 0	1	2	3	Very confident 4
------------------------------	---	---	---	---------------------

3. How confident are you in your ability to make the most of your visit with a doctor?
[maximize_visit](#)

Not at all confident 0	1	2	3	Very confident 4
------------------------------	---	---	---	---------------------

4. How confident are you in your ability to get a doctor to take your health concerns seriously?
[take_serious](#)

Not at all confident 0	1	2	3	Very confident 4
------------------------------	---	---	---	---------------------

5. How confident are you in your ability to get a doctor to do something about your health concerns?
[make_dr_act](#)

Not at all confident 0	1	2	3	Very confident 4
---------------------------	---	---	---	---------------------

6. How confident are you in your ability to ask a doctor questions? [able_to_ask](#)

Not at all confident 0	1	2	3	Very confident 4
---------------------------	---	---	---	---------------------

Emotional Support (Enriched Social Support Instrument)

1. Is there someone available to you whom you can count on to listen to you when you need to talk.
[count_on](#)

None of the time 0	A little of the time 1	Some of the time 2	Most of the time 3	All of the time 4
-----------------------	---------------------------	-----------------------	-----------------------	----------------------

2. Is there someone available to give you good advice about a problem. [good_advice](#)
3. Is there someone available to you who shows you love and affection? [shows_love](#)
4. Is there someone available to help you with daily chores? [help_chores](#)
5. Can you count on anyone to provide you with emotional support (taking over problems or helping you make a difficult decision)? [provide_support](#)
6. Do you have as much contact as you would like with someone who feel close to, someone in whom you can trust and confide? [desired_contact](#)
7. Are you currently married or living with a partner? [marital_status](#)

Tangible Support

In the last 3 months, have you needed any kind of extra help at home because your health kept you from taking care of yourself or doing what you usually do? [need_support](#)

- a. Yes
- b. No

IF YES:

Of the help you got at home, would you say you got: [amt_received_support](#)

- (1) All the help you needed
- (2) Most of the help you needed
- (3) Some of the help you needed
- (4) Only a little of the help you needed
- (5) None of the help that you needed

Demographic/Background Information

Next, I'd like to ask you a few questions about yourself.

1. **What year were you born ? _____**

2. **Which of these groups best represents your race? You can choose more than one answer.**
 - a. American Indian or Alaskan Native
 - b. Asian
 - c. Black or African American
 - d. Native Hawaiian or Other Pacific Islander
 - e. White or Caucasian

3. **Which of these groups best represents your ethnicity? You can choose more than one answer.**
 - a. Hispanic
 - b. Non-hispanic

4. **What is the highest level of education you have completed? *education***
 - a. Less than high school
 - b. Grade 12 or GED (High school graduate)
 - c. Technical school or associate's degree, 2 years
 - d. College 4 years or more (College graduate)
 - e. Advanced degree (Master's degree or Doctorate)

5. **What is your current employment status? *employed***
 - a. Currently employed
 - b. Retired
 - c. Unemployed
 - d. On disability

6. **When did you first learn you had heart failure? *hf_duration***
 - a. Less than 1 year ago
 - b. 1- 5 years ago
 - c. More than 5 years ago

Social Support Registry

1. Can we include your name and contact information on a list to call for future studies about social support or social relationships and chronic illness? *registry*

Yes

No

The following script will be used after the participant has completed their baseline data collection.

The next part of the study is to meet you at your next doctor's appointment at the heart clinic in Meadowmont. At this appointment you will receive a list of topics and questions that you and your family member will review and complete before your appointment. We will also audio record your appointment with your provider.

So that you have time to complete your list, we ask that you and your family member arrive 30 minutes before your scheduled appointment.

Do you know when your next appointment at the heart clinic at Meadowmont is?

[If yes] **Great, when is your appointment?**

Date _____

Time _____

Don't forget that your family member will need to join us for that appointment.

Will your family member be able to attend that appointment with you?

[if not or if the patient is unsure, ask the patient to follow up with the family member, the RA/SC should plan to follow up with the family member to remind them of the appointment as well]

I would like to call you 1 – 2 days before your appointment to remind you that I will be there.

Do you have a telephone number that I can reach you?

Great, thank you!

When would you prefer I call you to remind you of your appointment?

__ Morning __ Afternoon __ Evening __ Specific time _____

Again, we really appreciate you taking the time to participate in the study. For your time and participation on the study, you will receive a gift card.

[provide them with their gift card if in person]

[if baseline is completed over the phone, use the following script...]

When we meet at your appointment, I will provide you with your gift card for completing today's questions.

[hand them the PiH Study informational and contact sheet if in person or provide the information if over the phone]

Here is our information. Please contact us if you have any questions or if your appointment has been rescheduled.

Thank you for taking time to answer my questions today. I'll call you again a few days after your appointment with your heart doctor to ask some additional questions. I look forward to talking with you then. Have a great day!

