4 STUDY PROCEDURES

4. 1 Screening/Baseline Visit procedures: Thirty HF dyads will receive the prompt list. Each dyad member will receive a prompt list to complete in the clinic waiting room immediately before their appointment. HF dyads will complete the prompt list without staff help. Completing the prompt list involves two steps. In step 1, participants will independently select from a list of questions or write in their own questions they would like to ask their health care provider during the visit. Patients will also be asked to select among a pre-determined list of behaviors they would like their family member to engage in during the visit (e.g., write down the providers instructions). In step 2, dyad members will collaboratively decide which questions to discuss during the visit. Participants will be encouraged to take the prompt list into the exam room and use it to facilitate communication with the HCP. The RA may take a picture of the prompt lists (which will not contain any identifying information, only a study id) to assess areas of agreement and disagreement between the dyad on what to discuss with the HCP. This information will inform future studies.

Potential participants will be identified using several sources: the Carolina Data Warehouse (CDW-H); the HF social support and family studies registry (SSR; IRB #11-0562); medical record audits by the study PI; and suggestions from HCPs.

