After initial identification, we will query HCPs of potentially eligible patients to confirm the diagnosis of HF. (based on their clinical assessment), determine if the patients are appropriate to approach for possible study participation (procedures we have successfully used in our prior studies). When we provide participating providers with a list of their potentially eligible patients, we will all ask them to check how often the patient has a companion enter the exam room with them (none of the time, rarely, some visits, most visits, every visit). Patients will be considered "likely to be accompanied" if the provider indicates that a companion enters the exam room "most visits or every visit." We anticipate that the providers will be very accurate in predicting patients who usually bring a family member into the exam room, since these will be their regular patients. This method will be used to facilitate more efficient recruitment of patients most likely to be eligible for the study. For patients deemed ineligible by providers, we will ask providers to provide reasons why the patients should not be contacted, Provider approved patients will be approached by a research assistant (RA) to assess eligibility and possible interest in the study either during a scheduled clinic visit, via a provider-approved letter, or via telephone using an IRB approved telephone script. For those presenting for a clinic visit, the RA/SC will approach them about participation in the study. If they are interested, the study staff will consent the patient at that time and administer the baseline survey. If there isn't time to complete the entire baseline survey before the visit, we will finish the remainder of the survey either after the visit or via phone within the week of the visit.

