We will use several approaches to identify and enroll family members: 1) If a family member has accompanied the patient to the clinic visit, the family member will be approached by a study coordinator at that time about participation in the study and they can provide written consent at that time, if they are interested and eligible. They will also be administered the baseline survey either before (or after the visit depending on the time) or via phone in the week of the visit. 2) If a family member is not present with the patient at a clinic visit, an IRB-approved study recruitment letter and a copy of the consent form will be sent home with the patient to give to a family member who may be interested in participating, and the family member can contact a study coordinator to discuss the study and/or mail in the signed consent form. The study team will provide a pre-paid self-addressed envelope to return the signed consent form. After receiving signed consent form, the study team will call the potential participants to schedule the baseline study interview for both members of the dyad. For potential participants identified through the CDW or from the HF social support and family studies registry, the study team will mail an IRB approved recruitment letter to potential patient participants. The letter will notify the patient that a family member (preferably who one attends medical visits with them) is required to also participate in the intervention, so they should discuss the study with family members and get their permission to share their contact (phone number or address) with the study team. The letter will include an opt-out form that potential participants may return using pre-paid, self-addressed envelope that will accompany the recruitment letter. We will follow-up with potential patient participants via telephone 1 week after the letters have been mailed. If they are interested in participating and have identified a family member who is interested, the study team will obtain verbal consent from each person and a written consent form will also be mailed to them to sign and return to the study team. The RA/Project Coordinator will also schedule the baseline study interview. If the patient and family member provide verbal consent, but do not return the written consent form via mail, we will have them sign a written consent form at the time of baseline study interview. We will make it clear to the patient and family member that both individuals must be eligible and provide informed consent for either to be eligible to participate in the study. An RA/Study coordinator will obtain informed written consent for all eligible and interested dyads.

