"Family is broadly defined as two or more persons who are related in any – biologically, legally, or emotionally. Therefore, "family" is defined by the patient.

5. Do you think the patient considers you family?

YES NO

If "yes", confirm with the patient. If the patient does not agree then the individual is not eligible to participate.

IS THE INDIVIDUAL ELIGIBLE AS A FAMILY MEMBER? (Circle one)

ELIGIBLE INELIGIBLE

BASELINE ADMINISTRATION PROTOCOL

The following is protocol for the administration of the **BASELINE QUESTIONNAIRES** to study participants.

The baseline questionnaires can be collected in 3 different ways: 1) on the phone with the participant after the participant has provided verbal consent; 2) in person, after the participant has completed their informed consent; or 3) by phone after the participant has met with the RA/SC in person at a medical appointment at enrollment and completed their informed consent but did not have time to complete the baseline questionnaires.

After participants have consented (verbally or by in-person informed consent), the **BASELINE QUESTIONNAIRES** will be administered.

The RA/SC will need the following:

- iPad and power source for data collection into REDCap
- Paper copies of the questionnaire
- Answer key for the patient
- Pen/pencil for both the RA/SC and the subjects

Note: For iPad administration of the surveys, refer to the REDCap section in this protocol.

After the participant has provided consent, the RA/SC will administer the baseline questionnaires. It is important to speak clearly and slowly so that the participant can understand what is being asked, especially if the baseline data collection occurs over the phone.

Baseline data collection is preceded by the following prompt:

Hello, _____. This is [NAME] calling from UNC Health Care. I'm calling about the Heart Failure Study that you joined last week.

As a first step in the study, I'd like to ask you a few questions about your health and your healthcare experiences. Our conversation should take about 15 minutes. Is this a good time to talk?

[IF YES, PROCEED]

[IF NO, RESCHEDULE FOR A LATER DATE/TIME]

You are in this study because you have heart failure. Doctors sometimes call this congestive heart failure, an enlarged heart, or fluid in the lungs.

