During our conversation, I'll ask you questions about yourself, your visit companion, and your interactions with your doctor. Your "visit companion" is the family member or friend who comes with you to your health appointments. Your "doctor" is the doctor, nurse practitioner, or other health care provider who you usually see during your visit.

After completing the prompt and if the participant is able to conduct their data collection at that time, the RA/SC will collect their data either by using one of the following: 1) paper data collection materials; 2) the iPad REDCap application; or 3) by computer using the REDCap online data capture system. Regardless of the way in which the data is collected, each data collection will be administered uniformly to all participants.

Below are the **BASELINE QUESTIONNAIRES** with their respective variables for analysis for patients

List of measures included in this questionnaire:

1. Relationship with companion
2. Companion involvement
3. Closeness with companion
4. Health literacy
5. Knowledge of heart failure+
6. Self-care behaviors
7. Self-efficacy related to self-care
8. Perceived health status
9. Heart failure symptom severity
10. Communication with provider
11. Perceived efficacy in interactions with doctor
12. Perceived social support
13. Demographic/background questions

*Note that the Baseline Questionnaires **for companions** includes the following measures, which parallel the patient questionnaires:

List of measures included in this questionnaire:

1. Relationship with patient
2. Companion involvement
3. Closeness with patient
4. Knowledge of heart failure
5. Caregiver care behaviors
6. Self-efficacy related to patient care
7. Perceived efficacy in interactions with doctor
8. Demographics
9. Health literacy

Companion for visit with doctor

1. **Will you have a companion, such as a family member or friend, come with you to visit your doctor during this study? Variable name: accompanied**

- a. Yes
- b. No

IF NO:

- 2. Does someone usually go with you to your medical appointments? **Variable name: usual_accomp**
 - a. Yes
 - b. No

Relationship with Companion

[IF PARTICIPANT WILL NOT HAVE A COMPANION COME WITH THEM TO THEIR APPT, ASK ABOUT THE PERSON WHO USUALLY GOES WITH THEM. IF PARTICIPANT DOES NOT USUALLY HAVE A COMPANION COME WITH THEM TO THEIR APPT, SKIP AHEAD TO HEALTH LITERACY.]

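### Can the baseline outcome scales be completed after the prompt list has already been used?

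*Combined protocol and SAP*

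**What the plan says.** Section 4.1 begins "Screening/Baseline Visit procedures: Thirty HF dyads will receive the prompt list" and describes the dyad filling the list in before an appointment, without saying which appointment. It then covers identification, consent and the baseline survey. For a patient enrolled at a clinic visit who lacks time beforehand, "we will finish the remainder of the survey either after the visit or via phone within the week of the visit". An accompanying family member may be "administered the baseline survey either before (or after the visit depending on the time) or via phone in the week of the visit".

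The Baseline Administration Protocol names three ways of collecting baseline. The third is "by phone after the participant has met with the RA/SC in person at a medical appointment at enrollment", for people who did not have time on the day. The spoken introduction presents the questionnaire with the words "As a first step in the study". Its companion items look ahead: "Will you have a companion, such as a family member or friend, come with you to visit your doctor during this study" and "please think about the person who will come with you to your medical appointment during this study".

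The questionnaire ends with this instruction to staff: "The following script will be used after the participant has completed their baseline data collection". That script says the list will be given, and the consultation recorded, at the participant's following appointment at the heart clinic. It has branches for baseline done in person and by phone.

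Section 6.3 compares baseline with 1 month by paired t-tests, states that hypotheses are not being tested, and intends the effect sizes for planning later proposals.

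**The concern.** There is no control group, so nothing in the analysis would correct a baseline already moved by the list. Three features make the wording of 4.1 look risky.

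- List handover stands under a heading about screening and baseline, and the same section lets baseline run past the visit. If both refer to one visit, the list comes first.
- No sentence requires the outcome scales to be finished before the list is handed over.
- The patient outcome scales are measures 6, 7, 10 and 11 of 13, so an interrupted survey would tend to leave them for later.

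A post-list baseline would matter most for self-care confidence and perceived efficacy with the doctor, which ask about the present. It would matter less for the self-care behaviours (past month) and communication items (usual practice). If the list helps quickly, the change would be understated; if the visit lowered scores, it would be overstated.

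**Working it through.** The documents give no figure to reproduce. The question is the order of events, so the check compares the places that describe it and then sizes the effect if the order failed.

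**1. Is section 4.1 chronological?** No. Its list paragraph comes before participants are identified, screened or consented. Taken as a sequence, people would complete the list before being found. Nearly the same paragraph reappears under the second section numbered 4.1 (Intervention/Treatment procedures), headed as the patient's medical appointment. The first occurrence is best read as a summary of the intervention.

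**2. What happens to someone whose baseline is late?** This case has its own route, mode 3 of the Baseline Administration Protocol: enrolled at an appointment, surveyed later by phone. The phone introduction refers to a study joined the week before and still calls baseline the first step. The closing script then places the list at the following appointment. For this participant the order is enrolment visit, baseline by phone, list visit.

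**3. Do other sections agree?**
- Section 10 lists baseline, the appointment day, the 2-day call and the 1-month call as separate collection points.
- The visit-day procedure hands over the gift card earned for baseline, which presumes baseline is done.
- Section 4.6 allows up to 6 months of participation. With 1 month taken as 30 days, the list visit may fall as late as 183 − 30 − 7 = 146 days after enrolment with the full follow-up window still inside the limit. A one-visit path would end by day 30 + 7 = 37.

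**4. Does a one-visit reading fit the windows?** Poorly. Counting from a shared visit, the 2-day call falls on days 0 to 4, a late baseline could run to about day 7, and the 1-month call falls on days 23 to 37. A baseline could then follow the 2-day call and precede the 1-month call by only 16 to 30 days (23 − 7 and 37 − 7). The timings on the day fit no better: baseline is expected to take about 15 minutes, while dyads are asked to arrive 30 minutes early for the list. A visit too rushed for the survey is unlikely to have room for the list.

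**5. Size if the order failed.** Let f be the share of dyads with post-list scales and g the share of the 1-month effect already present then. Neither is in the documents. Observed change ÷ true change = 1 − f × g.

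| f | g | ratio |
|---|---|---|
| 0 (scripted order) | any | 1 |
| 0.10 | 0.25 | 0.975 |
| 0.25 | 0.50 | 0.875 |
| 0.50 | 1 | 0.50 |
| 1 | 1 | 0 |
| 0.25 | −0.25 | 1.0625 |

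For an assumed standardised change of 0.50 and 30 pairs (the stated maximum), the 95% half-width is 1.96 × √(1/30 + 0.25/60) = 0.38. The loss, 0.50 × f × g, exceeds this only if f × g is above 0.38/0.50 = 0.76. The table runs from no effect to total loss and can change sign, so it says nothing about this trial beyond its first row.

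**The case for a change.** The best case for acting is that a script does not override a procedures section. A coordinator working from 4.1 alone could hand out the list at enrolment and telephone for the rest of the survey. The intervention section also allows consent to be taken just before the recorded visit, which seems to leave a one-visit path open. One sentence, with the outcome scales asked first and two times recorded, would protect the pilot's only effect estimate cheaply.

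Part of this stands. Section 4.1 does not name the appointment, its heading is careless, and no sentence explicitly puts the outcome scales before the list. The rest is weaker. The questionnaire and scripts are printed in the same section of the protocol and are what staff hold when they speak to participants; the closing script is written as mandatory for in-person and phone baselines alike. The consent note has an ordinary explanation within the two-visit path: baseline may be done by phone on verbal consent, and section 4.1 foresees that mailed written forms may not come back. Once the order is baseline then list, reordering the instruments, recording handover times and a sensitivity analysis have nothing to act on.

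**Conclusion.** No change is needed. Late completion of baseline is a sensible allowance for busy clinics, and under the scripted sequence it still falls before the list. The bias in the baseline-to-1-month change is then zero. This rests on staff following the baseline protocol and its closing script, which section 10 and the visit-day procedure support; the documents cannot show what happened in practice. Any other size depends on assumed values of f and g. Even a departure would leave the enrolment and acceptability endpoints untouched and would affect only estimates that section 6.3 presents for planning. What remains is loose wording in 4.1, which the rest of the protocol resolves.
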